- q* The daily diaries will be filled out by patients at home for 7 days prior to baseline visit and after that at home for consecutive days for the specified administration period before the study visits and will be collected at the time of visit.
- r* The PROs will be administered to patients at study visit according to the listed schedule.
- s* Prior to the start of IMP at Baseline Visit. In subjects who have consented to it, samples of serum will be collected and archived for future analysis.

- t* All SAEs, AEs and AEs of special interest (AESIs) will be collected starting with signing informed consent and continue until 30 days after the last dose of IMP or study end, whichever comes later. All AEs that occurred during treatment should be followed for at least 30 days following the last dose of IMP or until the event has resolved, the condition has stabilized, the etiology of the event is determined to be not related to IMP, or the patient is lost to follow-up. All patients should be followed to collect safety information up to 30 days after the last IMP administration or up to the first visit of the long-term extension study, whichever occurs first. For patients enrolled or screened into the long-term extension study prior to 30 days after the last dose of IMP, all SAEs, AEs, and AESIs will be collected up to the last visit in Study EFC15392, which will coincide with the first visit in the long-term extension study. Details of ongoing AEs and ongoing medications at the time of the last visit in Study EFC15392 will be duplicated as such into the long-term extension study.
- u* The initial screening period (Visit 1) can last up to 15 days (+3 days). Visit 2 can be performed as soon as results of all assessments performed at Visit 1 are available.
- v* During the run-in period the patient will receive single-blind placebo.
- w* At Visit 12 patients may be offered to enter long-term extension study. For patients who will agree and will be eligible to enter into a potential long-term extension study without any discontinuation between the EFC15392 and the LTS15823 studies, Visit 12 (end of treatment visit) of EFC15392 study will correspond to Visit 1 of LTS15823 study including all planned evaluations to be performed at Visit 12 of EFC15392 study and an additional MRI that will be performed in the frame of Visit 1 of the LTS15823 study.

#### 1.4 STUDY FLOW CHART FOR STAGE 2

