## **6.2 DURATION OF STUDY PARTICIPATION**

### **6.2.1 Duration of study participation for each patient**

The maximum study duration per patient will be approximately 26 months.

This will consist of a screening period of up to 30 +3 days (initial screening period of up to 15 +3 days and single-blind placebo run-in period of 15 ±3 days), followed by a blinded study core treatment period of 24 months and a 30-day follow-up visit (for patients not participating in the potential long-term extension study) after the final dose of investigational medicinal product (IMP).

Patients who completed 24 months of treatment in EFC15392 study may be given the option to enroll into an open-label long-term extension study LTS15823 (additional 24 months of treatment with 15 mg venglustat [ie, as specified in the EFC15392 protocol the dose selected for Stage 2 of EFC15392 study during unblinded review by the DMC of the aggregated safety data for 150 patients who have completed at least 1 month of treatment in EFC15392 study]).

The last study visit:

1. for patients who elect to enter the potential long-term extension study upon completion of 24 months of treatment in EFC15392 study will be Visit 12 (Month 24)
2. for patients who complete the treatment in EFC15392 study and elect not to enter this potential extension study will be Visit 13 (Month 25)
3. for patients who permanently discontinue medication and continue for all the remaining visits will be Visit 12 (Month 24) if they continue for all the remaining visits, or it will be their premature follow-up visit.

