- I 09. Female patients of childbearing potential and male patients must agree to practice true abstinence in line with their preferred and usual lifestyle or to use double-contraceptive methods (including a highly effective method of contraception for female patients of childbearing potential) for the entire duration of the study and for at least 6 weeks for females and 90 days for males following their last dose of study drug (see contraceptive guidance in [Appendix A](#)).

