#### **10.4.2 General guidelines for reporting adverse events**

- All AEs, regardless of seriousness or relationship to IMP, spanning from the signature of the informed consent form until the end of the study as defined by the protocol for that patient, are to be recorded on the corresponding page(s) or screen(s) of the eCRF.
- Whenever possible, diagnosis or single syndrome should be reported instead of symptoms. The Investigator should specify the date of onset, intensity, action taken with respect to IMP, corrective treatment/therapy given, additional investigations performed, outcome, and his/her opinion as to whether there is a reasonable possibility that the AE was caused by the IMP or by the study procedure(s).
- The Investigator should take appropriate measures to follow all AEs until clinical recovery is complete and laboratory results have returned to normal, or until progression has been stabilized, or until death, in order to ensure the safety of the patients. This may imply that observations will continue beyond the last planned visit per protocol, and that additional investigations may be requested by the monitoring team up to as noticed by the Sponsor. At the prespecified study end-date, patients who experience an ongoing SAE or an AESI should be followed until resolution, stabilization, or death and related data will be collected.

- When treatment is prematurely discontinued, the patient's observations will continue until the end of the study as defined by the protocol for that patient.
- Laboratory, vital signs, ECG, or ophthalmic examination abnormalities are to be recorded as AEs only if:
  - Symptomatic and/or,
  - Requiring either corrective treatment or consultation, and/or,
  - Leading to IMP discontinuation or modification of dosing, and/or,
  - Fulfilling a seriousness criterion, and/or,
  - Defined as an AESI, and or,
  - Leading to unscheduled full ophthalmological examination with or without WHO simplified cataract grading system evaluation.

Instructions for AE reporting are summarized in [Table 4](#).

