#### Note:

- a Typical use failure rates may differ from those when used consistently and correctly. Use should be consistent with local regulations regarding the use of contraceptive methods for patients participating in clinical studies.
- b Hormonal contraception may be susceptible to interaction with the study treatment, which may reduce the efficacy of the contraceptive method. In this case 2 highly effective methods of contraception should be utilized during the treatment period and for at least 6 weeks for females and 90 days for males following their last dose of study drug.

Male patients with partners of reproductive potential who become pregnant:

- The Investigator will attempt to collect pregnancy information on any female partner of a male study patient who becomes pregnant while participating in this study. This applies only to patients who receive study treatment.
- After obtaining the necessary signed informed consent from the pregnant female partner directly, the Investigator will record pregnancy information on the appropriate form and submit it to the Sponsor within 24 hours of learning of the partner's pregnancy.
- Partner will also be followed to determine the outcome of the pregnancy. Information on the status of the mother and child will be forwarded to the Sponsor.
- Generally, follow-up will be no longer than 6 to 8 weeks following the estimated delivery date. Any termination of the pregnancy will be reported regardless of fetal status (presence or absence of anomalies) or indication for procedure.

Female patients who become pregnant:

- The Investigator will collect pregnancy information on any female patient, who becomes pregnant while participating in this study.
- Information will be recorded on the appropriate form and submitted to the Sponsor within 24 hours of learning of a patient's pregnancy.
- Patient will be followed to determine the outcome of the pregnancy. The Investigator will collect follow-up information on patient and neonate, which will be forwarded to the Sponsor. Generally, follow-up will not be required for longer than 6 to 8 weeks beyond the estimated delivery date.
- Additional follow-up information may be requested about the baby until at least 1 year after the birth of the baby, due to potential risk of abnormalities not present at birth.
- Any termination of pregnancy will be reported, regardless of fetal status (presence or absence of anomalies) or indication for procedure.

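### For patients who leave at the 30-day follow-up visit, required pregnancy reporting stops before the protocol's own contraception period ends (6 weeks for women, 90 days for men)

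*Protocol*

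**What the plan says.** **Contraception period.** Protocol 7.1, I 09, requires contraception "for at least 6 weeks for females and 90 days for males following their last dose of study drug". Appendix A repeats both periods.

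**Status of pregnancy.** Section 10.4.1.3 makes pregnancy in a female patient, or in a male patient's partner, an adverse event of special interest (AESI). Follow-up to outcome is mandatory.

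**Collection period.** Footnote t of both flow charts (1.3 and 1.4) gives two rules. AEs, SAEs and AESIs "continue until 30 days after the last dose of IMP or study end, whichever comes later". Two sentences later it says "All patients should be followed to collect safety information up to 30 days after the last IMP administration", and the full limit there is "up to 30 days after the last IMP administration or up to the first visit of the long-term extension study, whichever occurs first". Section 10.4.2 sets the AE recording period as "spanning from the signature of the informed consent form until the end of the study as defined by the protocol for that patient".

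**Last visit.** Under Section 6.2.1, completers who do not enter the extension finish at Visit 13 (Month 25). For those who stop treatment early, the last visit "will be Visit 12 (Month 24) if they continue for all the remaining visits, or it will be their premature follow-up visit". Section 10.1.3 allows Visit 13 to fall from 7 days before to 21 days after Day 750.

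**Scope of pregnancy collection.** Appendix A covers a female patient who becomes pregnant during participation, and "any female partner of a male study patient who becomes pregnant while participating in this study". After the study, a pregnancy-related SAE judged related is reportable if the investigator learns of it, with no obligation to look for it.

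**SAP.** Section 4.1 ends the treatment-emergent period at 30 days after the last dose or the first extension visit, whichever is earlier. Table 7 includes a post-treatment AE overview, whose footnote lists AESIs among the categories counted. Table 8 takes pregnancies from a dedicated e-CRF page.

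**The concern.** The protocol treats pregnancy as important enough for 24-hour reporting and mandatory outcome follow-up, and it asks patients to prevent pregnancy for a stated time after the last dose. Its reporting arrangements end sooner for some patients. A conception after the last contact but inside the contraception period would reach the database only if someone volunteered it.

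At stake is the completeness of the pregnancy AESI and of the outcome data that depend on it, since a pregnancy that nobody learns of cannot be followed. The gap is widest for partners of male patients, whose period is the longer one. The two sentences of footnote t add to the problem because sites could read the end of collection differently.

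**Working it through.** No sample size, power or alpha figure is involved, and the plan states no figure to reproduce. The check subtracts the documents' own day counts.

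**Inputs**
- Contraception period after the last dose (I 09): 6 weeks = 42 days for women, 90 days for men.
- Last dose for a completer: taken as Day 720 (Visit 12).
- Visit 13 (Section 10.1.3): Day 750, from −7 to +21 days, so Day 743 to Day 771.

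**Days from last dose to last planned contact**
- Nominal: 750 − 720 = 30
- Earliest: 743 − 720 = 23
- Latest: 771 − 720 = 51

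**Uncovered days = contraception period − days to last contact, with a floor of 0**

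| | Nominal | Visit 13 earliest | Visit 13 latest |
|---|---|---|---|
| Women (42 days) | 42 − 30 = 12 | 42 − 23 = 19 | 42 − 51 < 0, so 0 |
| Partners of male patients (90 days) | 90 − 30 = 60 | 90 − 23 = 67 | 90 − 51 = 39 |

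As shares of the period, the nominal gaps are 12/42 = 29% and 60/90 = 67%. The women's gap closes only when Visit 13 falls at least 42 days after the last dose. The men's gap remains at every permitted date.

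**Who this applies to**
- Completers outside the extension: yes, because Visit 13 is their last visit.
- Early discontinuers whose last visit is the premature follow-up: yes. Flow chart footnote a places that visit 30 days after the last dose, so the nominal figures apply.
- Early discontinuers who keep attending to Month 24: they can be observed well past 90 days, depending on when they stopped.
- Extension entrants: they pass into the other study's safety collection.

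**Footnote t**
- If study end in its first sentence means the individual patient's end, as Section 10.4.2 suggests, that is Visit 13 for a completer outside the extension. Collection then ends at the later of day 30 and Visit 13.
- If it means the end of the whole trial (Section 6.2.2), collection could run much longer, but no contact is scheduled to support it.
- The later sentence stops at 30 days at most. Under that rule a late Visit 13 does not extend follow-up, and the women's gap stays at 12 days.

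Neither rule is tied to the periods in I 09.

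**The case against.** The strongest reply is that the protocol does not simply stop at 30 days. Footnote t's first sentence takes the later of 30 days and study end, discontinuers are asked to attend to Month 24, and extension entrants remain under observation. Section 10.4.1.3 sets no day limit in its definition and makes outcome follow-up mandatory. This stands, and it confines the point to the two groups above and to pregnancies that nobody is required to look for. It does not close the gap for those groups.

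It can also be said that a contraception period and a surveillance period need not be equal. That is fair. The visible text gives a contraception duration without a reason for its length, and parts of Section 4.3 are not shown. The protocol could justify a shorter reporting period, but the visible text does not do so.

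Four stronger readings are tempting, and the documents do not support them.
- **That all later pregnancies are lost or get no outcome follow-up.** One that becomes known is still covered by 10.4.1.3, and related post-study SAEs remain reportable.
- **That the blank pregnancy-test cell at Visit 13 causes the gap.** A day-30 test cannot detect conceptions on days 31 to 42 and says nothing about partners. Home tests for monthly use are also supplied at visits that include Visit 12.
- **That a number of missed pregnancies can be given.** The documents state neither the split by sex nor a pregnancy rate, and 280 of the 640 planned patients (80 + 200) are on placebo.
- **That the study-wide stop put every participant into the gap.** Patients never dosed, or who stopped more than 90 days earlier, were not in it. The SAP version history does record that both this study and the extension were discontinued, so the extension cannot be assumed to cover everyone.

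**Conclusion.** The point holds for completers outside the extension and for early discontinuers whose last visit is the premature follow-up. For them, required pregnancy collection ends about 30 days after the last dose, inside the contraception period the protocol sets. The size is 12 days for women (0 to 19) and 60 days for partners of male patients (39 to 67). It rests on a last dose at Day 720 and on Visit 13, or its premature equivalent, being the last planned contact.

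The internal conflict in footnote t holds without any assumption. No claim is made about how many pregnancies would be missed or about the right length of the contraception periods. Efficacy analyses are unaffected.

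**What to change.** - Reconcile the pregnancy-AESI collection period in footnote t (both flow charts), Section 10.4.1.3 and Appendix A with the contraception period in I 09. If a shorter reporting period is intended, give the reason.
- Reconcile the two sentences of footnote t with each other and with Section 10.4.2, and make clear whether study end means the patient's or the trial's.
- Report pregnancies identified after the treatment-emergent period in the SAP's post-treatment overview, which already counts AESIs. The treatment-emergent definition need not change.

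The cost is protocol wording and at most one brief contact for each patient outside the extension whose visits end before the period in I 09. The pregnancy e-CRF page already exists.

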### 3 LIST OF ABBREVIATIONS

ADMA:	asymmetric dimethylarginine
ADPKD:	autosomal dominant polycystic kidney disease
AE:	adverse event
AEs:	adverse events
AESI:	adverse event of special interest
ALP:	alkaline phosphatase
ALT:	alanine aminotransferase
anti-HCV:	anti-hepatitis C
anti-HIV1:	anti-human immunodeficiency virus 1 antibody
anti-HIV2 Ab:	anti-human human immunodeficiency virus 2 antibody
AST:	aspartate aminotransferase
AUC:	area under the concentration-time curve
BCVA:	best corrected visual acuity
BDI-II:	beck depression inventory II
BFI-SF:	brief fatigue inventory short form
BPI-SF:	brief pain inventory short form
BUN:	blood urea nitrogen
CDMS:	clinical data management system
CI:	confidence intervals
CKD:	chronic kidney disease
CKD-EPI:	Chronic Kidney Disease Epidemiology Collaboration
CL ss :	clearance at steady state
C max :	maximum observed concentration
CNS:	central nervous system
COR-2:	cortical cataract-2
DBP:	diastolic blood pressure
DMC:	Data Monitoring Committee
DNA:	deoxyribonucleic acid
eCRF:	electronic case report form
eGFR:	estimated glomerular filtration rate
EOT:	end-of-treatment
EQ-5D-5L:	European quality of life 5-dimension 5-level
EU:	European Union
FD:	Fabry disease
fe:	mean fraction of dose excreted unchanged in urine
FGF23:	fibroblast growth factor 23
FSH:	follicle stimulating hormone
GBA:	glucocerebrosidase
GBA-PD:	Parkinson's disease with a confirmed acid-β-glucosidase gene mutation, glucocerebrosidase in Parkinson Disease
GCP:	Good Clinical Practice

GCS:	glucosylceramide synthase
GD:	Gaucher disease
GD3:	Gaucher Disease Type 3
GGT:	gamma-glutamyl transferase
GI:	gastrointestinal
GL-1:	glucosylceramide
GL-2:	lactosylceramide
GL-3:	globotriaosylceramide
GM3:	monosialodihexosylganglioside
GSL:	glycosphingolipids
GSL:	glycosphingolipid
HBcAb:	hepatitis C core antibody
HBsAb:	hepatitis B surface antibody
HBsAg:	hepatitis B surface antigen
hERG:	human ether-a-go-go-related gene
HLGT:	high-level group term
HLT:	high level term
IB:	investigator's brochure
IEC:	Independent Ethics Committee
IMP:	investigational medicinal product
INR:	International Normalized Ratio
IRB:	Institutional Review Board
IRT:	interactive response technology
ITT:	Intent-to-treat
LC-MS/MS:	liquid chromatography tandem mass spectrometry
LLOQ:	lower limit of quantification
MCP-1:	monocyte chemoattractant protein-1
MedDRA:	Medical Dictionary for Regulatory Activities
mGFR:	measured glomerular filtration rate
MMRM:	mixed effect model with repeated measures
MMSE:	mini mental state examination
MRI:	magnetic resonance imaging
NOAEL:	no observed adverse effect level
NRS:	numeric rating scale
NYHA:	New York Heart Association
PCSA:	potentially clinically significant abnormality
PD:	pharmacodynamic
PGIC:	patient global impression of change
PGIS:	patient global impression of severity
PK:	pharmacokinetic(s)
PR interval:	the time from the onset of the P wave to the start of the QRS complex
PRO:	patient reported outcome
PSC-2:	posterior subcapsular cataract-2
PT:	prothrombin time, preferred term
PTT:	partial thromboplastin time
QD:	once daily

QRS interval:	time from ECG Q wave to the end of the s wave corresponding to ventricular depolarization
RAAS:	renin-angiotensin-aldosterone system
SA:	statistical analysis plan
SAEs:	serious adverse events
SAR:	suspected adverse reaction
SBP:	systolic blood pressure
SC:	Steering Committee
SE:	standard errors
SMQ:	standardized MedDRA query
SOC:	system organ class, system organ class
SRT:	substrate reduction therapy
ST deviation:	ECG ST-segment deviation
SUSAR:	Suspected Unexpected Serious Adverse Reaction
TEAE:	treatment-emergent adverse event
TKV:	total kidney volume
$t_{\max}$ :	time to maximum observed concentration
ULN:	upper limit of normal
US:	United States
WHO:	World Health Organization
WOCBP:	women of childbearing potential
$\beta$ -hCG:	beta human chorionic gonadotropin

## 4 INTRODUCTION AND RATIONALE

### 4.1 BACKGROUND: VENGLUSTAT AND AUTOSOMAL DOMINANT POLYCYSTIC KIDNEY DISEASE

#### 4.1.1 Venglustat

GZ402671, also referred to as venglustat, SAR402671 is a glucosylceramide synthase (GCS) inhibitor that decreases the synthesis of glucosylceramide (GL-1), a central building block for more complex glycosphingolipids (GSLs). Substrate reduction therapy (SRT) with GCS inhibitors is expected to have broad therapeutic applicability across a number of disorders, including lysosomal storage diseases, as well as other disorders associated with increased GL-1 or increased levels of glycosphingolipids that contain GL-1 at their core.

Sanofi is investigating venglustat as a potential SRT for treating patients with Fabry disease (FD), Gaucher disease Type 3 (GD3), Parkinson's disease patients with a confirmed acid- $\beta$ -glucosidase (glucocerebrosidase gene [GBA]) mutation (GBA-PD), GM2 gangliosidosis, and autosomal dominant polycystic kidney disease (ADPKD). A novel GCS inhibitor, venglustat inhibits the enzymatic conversion of ceramide to GL-1, the first step in glycosphingolipid biosynthesis. By reducing the production of GL-1, the central building block for the synthesis of more complex glycosphingolipids (including globotriaosylceramide [GL-3], GM1, GM2, and monosialodihexosylganglioside [GM3]), SRT with venglustat offers a potential therapeutic strategy for FD, GD, GBA-PD, and ADPKD.

Venglustat is a potent and selective inhibitor of murine and human GCS in biochemical and cell-based in vitro assays. In vivo pharmacology studies in rodents and dogs showed reduction in plasma GL-1 concentrations as a pharmacodynamic (PD) marker of GCS inhibition. Reductions of GL-1 concentrations in plasma (rodents and dogs) and tissue (rodents only) were observed following oral venglustat administration. In both species, the effects of venglustat on plasma GL-1 were dose-dependent and correlated with plasma concentrations of the compound. Based on multiple preclinical studies following a single oral administration to rats, venglustat distributed extensively in kidney, liver, lung, spleen, intestine, and heart tissues and crossed the blood brain barrier.

#### 4.1.2 Autosomal dominant polycystic kidney disease

Autosomal dominant polycystic kidney disease (ADPKD) is a life-threatening genetic disease caused by mutations in PKD1 and PKD2 genes characterized by the formation of multiple kidney cysts that enlarge with disease progression to result in end-stage renal disease and dialysis in ~50% of patients (1). Cysts may also develop in liver and other organs (eg, seminal vesicle, pancreas). At least 60% of ADPKD patients report pain (back pain and abdominal pain) and up to one third of patients report severe symptoms. The target population is those patients with ADPKD at high risk of progressing to end-stage renal disease (1C, 1D, and 1E of the Mayo Imaging Classification). Classes 1C, 1D, and 1E represent 30% to 40% of the diagnosed ADPKD population who can be identified by imaging measures of kidney size (2, 3). In the United States (US), the diagnosed patient population is estimated to be between 1 in 2500 to 1 in 3000 or roughly 120 000 people which qualifies for an orphan designation (prevalence of less than 200 000). In the European Union (EU), the population is estimated to be approximately 170 000 people or 3.2 in 10 000 people. This is below the EU ceiling for orphan designation 5 in 10 000 (1).

Tolvaptan is approved in Japan, EU, US, and Canada to slow the progression of cyst development and renal insufficiency. The liver toxicity led to the requirement in the EU for a risk management plan which includes 18 months of monthly monitoring of the liver function (4). Tolvaptan safety (risk of idiosyncratic liver toxicity) and tolerability (eg, thirst, polyuria, and nocturia in ~55%, 38%, and 29% of patients, respectively) make it a suboptimal chronic treatment. In clinical studies, treatment discontinuation rates were 23% for tolvaptan and 14% for placebo, primarily due to adverse events (AEs).

The completion of the HALT-PKD study provided important insights to the management of hypertension in ADPKD (5). The HALT-PKD study, a US multicenter trial conducted on more than 1000 ADPKD patients with up to 8 years of follow-up, advised strict blood pressure control. In patients with estimated glomerular filtration rate (eGFR) above 60 mL/min/1.73 m^2, a target blood pressure of 110/70 mmHg was suggested, especially in young patients with a high progression risk. In chronic kidney disease (CKD) Stage 3, the target blood pressure should be below 120/80 mmHg. Double renin-angiotensin-aldosterone system (RAAS) blockade with a target blood pressure of 120/80 mmHg or less had no beneficial effects but did increase complications among older ADPKD patients (6). There is a significant variation in the local standard of care for blood pressure target and the use of therapeutic agent to achieve that.

It is generally advised to reduce dietary sodium intake to within limits recommended for the general healthy population, and general CKD population (<100 mmol/d). Increased fluid intake has been hypothesized to reduce the progression of ADPKD, but there is no direct evidence to

[figure not shown]
support this as a conclusive recommendation for use in clinical practice (7). In addition, since urinary osmolality is an endpoint in this trial, increase in fluid intake has not been recommended beyond normal daily fluid intake.

